**DATE: - 04/07/2022**

## **Introduction and Background**

Frozen shoulder is characterized by painful limitation of active and passive range of motion (ROM) of the shoulder. People describe pain, which can be severe, an inability to sleep on the affected side, loss of shoulder function in activities of daily living and limited movements that can lead to chronic stiffness.

Physiotherapy is one of the main treatments which aims to reduce pain, and regain mobility, muscle strength and optimal daily function. There is global loss of both passive and active ROM of the glenohumeral joint, with external rotation usually being the most restricted physiologic movement. Although frozen shoulder is frequently described as a self-limiting condition with gradual spontaneous recovery, the condition typically has mean duration of 30 months.

Individuals with primary frozen shoulder are commonly between 40 and 65 years old, and the incidence appears 4 times higher in females than males. The condition generally presents unilaterally with the non-dominant shoulder more commonly affected.

Frozen shoulder is “a condition difficult to define, difficult to treat, and difficult to explain from the point of view of pathology(Codman 1935) . The term adhesive capsulitis was introduced by Nevaiser to describe the inflamed and fibrotic condition of the capsule sticking to the humerus. But this term does not appear to appropriately describe the condition and arguably term should be abandoned as explained by Lundberg (1979).

The etiological explanation of frozen shoulder was directed toward two theories, contraction of the capsule and adhesions of the capsule which were running parallel. Some histological findings show that there is contraction of the capsule. In 1969, Lundberg came with the term frozen shoulder syndrome. In 2014, Jeremy Lewis came out with the term frozen shoulder contraction syndrome. It is likely that limitations in range of motion and the pain associated with frozen shoulder are not only related to capsular and ligamentous tightness, but also fascial restrictions, muscular tightness, and trigger points within the muscles. Physical therapists can address impairments and limitations associated each of these contributors to the pathology of frozen shoulder with a variety of treatment methods.

A meta-analysis suggested that glucocorticoid injections combined with exercise and manual therapy may provide improvement in range of motion .

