Intensive mobilization may be more effective than other methods but mostly for late stages of the disease. Rehabilitation programs consisting of exercise, and modalities have been shown to improve shoulder ROM in all planes except external and internal rotation .

One study also showed that supervised neglect physical therapy worked better than intensive physical therapy .

A 2013 RCT showed short term improvement in function and range of motion in the painful phase using intra-articular corticosteroid . A 2016 study showed adding mobilisation to stretching patients had a long-term improvement in function and passive range of motion at one year follow up .

In a review of 31 studies in 2012, Maund et al concluded that there is limited clinical evidence on the effectiveness of treatments for primary frozen shoulder .

The UK FROST trial compared early structured physiotherapy, manipulation under anesthesia and arthroscopic capsular release. All three treatment options led to substantial improvements in pain and function and none of the treatments were superior to each other in the long term follow up

A recent study by Hollmann et al (2018) has demonstrated that muscle guarding may be a significant contributing factor to shoulder movement deficits in some patients suffering from frozen shoulder. In a sample of five patients with an indication for capsulotomy, they found that under general anesthesia, the movement of the affected shoulder was less restricted. All patients showed a significant increase in their passive range of motion (ROM), especially in abduction while under general anesthesia conditions, compared to their ROM while awake.

This finding supports the hypotheses that the fear of pain or the fact that little used tissue can be more easily damaged can produce a fear-based brain reaction and generate a muscle defense response that could lead to Frozen Shoulder. So, this may be the major contributing factor to movement restriction in some of these patients although more research is needed to determine the number of patients suffering from this type of Frozen shoulder.

One study by Donatelli et al shows promising results with low load prolonged stretch in frozen shoulder but there is no evidence for high load training.

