## **Sample size**

Shoulder external rotation range of motion is considered as the primary outcome measure for the proposed study. A study by Celik (2010) [24] was used to inform the sample size calculation, where the shoulder external rotation was measured at baseline and at 12-week post intervention for the glenohumeral range of motion exercise group. Using the means and standard deviations of 22 (12.5) degrees and 33 (14.9) degrees for external rotation range of motion changes resulted in an effect size of -0.799. With a two tailed hypothesis, the minimum required sample size is 30 patients per group at ( $\alpha$ ) 0.05 and a power (1-  $\beta$ ) of 85%. 35 participants per group will be recruited to account for attrition.

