## **Randomization/Blinding**

Participants will be randomly assigned following simple envelope randomization procedures to one of the two treatment groups. Patients will be blinded from the treatment group, and the examinations will be performed by a blinded examiner.

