## **Intervention**

Both groups will receive conventional therapy sessions which include active ROM exercise, strengthening and stretching exercises, end-range mobilization and hot packs (if indicated). Exercises will be given within the pain threshold limit twice a week for 12 weeks. In addition, the experimental group will receive heavy slow resistance exercise program using a theratube. The exact management approach will be standardized between the two groups in terms of intensity and frequency and the experimental group will only receive additional heavy slow resistance exercise.

Subjects will be assessed at baseline and at 3, 6, and 12 months. Shoulder external rotation and abduction ROM will be measured and compared within and between groups and will be analyzed using a One-way ANOVA.

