## **Inclusion Criteria**

Inclusion criteria are males and females, Kuwaiti and non-Kuwaiti between 40 and 65 years with unilateral painful, restricted active and passive range of motion of the shoulder, with loss of passive external rotation of at least 50% compared to opposite side at 0 degrees of abduction and with normal X ray findings ]. Patients will be included if symptoms present for at least 3 months (Cyriax, 1993; Griggs et al., 2000).

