**Data analysis**

SPSS will be used for statistical analysis. All outcome measures will be analyzed using one-way ANOVA.

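### Symptom duration has a 3-month floor and no stated ceiling, and the unadjusted one-way ANOVA gives up some precision by ignoring it (valid comparison, cheap improvement, low priority)

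*Protocol*

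**What the plan says.** On entry, the protocol's Inclusion Criteria state "Patients will be included if symptoms present for at least 3 months". Neither that section nor the Exclusion Criteria sets a maximum. The same inclusion paragraph also requires a restricted shoulder, "with loss of passive external rotation of at least 50% compared to opposite side at 0 degrees of abduction".

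On natural history, the Introduction and Background says "Although frozen shoulder is frequently described as a self-limiting condition with gradual spontaneous recovery, the condition typically has mean duration of 30 months". On response by stage, it says "Intensive mobilization may be more effective than other methods but mostly for late stages of the disease". End-range mobilisation is part of the conventional therapy that both arms receive (Intervention).

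On design and analysis:
- Randomization/Blinding: "Participants will be randomly assigned following simple envelope randomization procedures to one of the two treatment groups". No stratification is named.
- Intervention: "Subjects will be assessed at baseline and at 3, 6, and 12 months", with external rotation and abduction compared by one-way ANOVA.
- Data analysis: "All outcome measures will be analyzed using one-way ANOVA".

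**The concern.** Two shoulders that are equally stiff at entry, one symptomatic for 3 months and the other for 24, both qualify. In a condition with a mean duration of 30 months, they may well change by different amounts over the next 12 months, whichever arm they are in. Duration has to be asked about to apply the entry rule, so it is available before randomisation. A one-way ANOVA has group as its only factor and cannot use it.

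Two things follow if duration is prognostic. Its spread stays in the error term and widens the interval for the difference between arms. With about 35 patients per arm and no stratification, the arms can also differ in duration by chance, and the unadjusted estimate carries that difference.

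This is not a complaint about detail left to a later analysis plan. The protocol names its method for all outcomes, and a plan that added a covariate would depart from it.

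**Working it through.** **Inputs from the protocol (Sample size).** "Using the means and standard deviations of 22 (12.5) degrees and 33 (14.9) degrees for external rotation range of motion changes"; two-sided alpha 0.05; power 85%; 30 per group, 35 recruited. These values are taken at face value here.

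**Inputs assumed, because the documents give none.** The partial correlation r of duration with follow-up external rotation is 0.2, 0.3 or 0.4. Half of the patients are late-stage.

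**1. The plan's own figure.** Pooled SD = sqrt((12.5² + 14.9²)/2) = 13.75. Difference = 33 − 22 = 11. Effect size = 11/13.75 = 0.80, as stated apart from sign and rounding. The two-sample t test needs 29.1 per group, rounded up to 30, where power is 86.1%. The stated number reproduces; it has no term for duration.

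**2. Precision gained by adjusting.** The share of residual variance removed is r². The unadjusted sample size equivalent to an adjusted 30 is 30/(1 − r²). The interval narrows by the factor sqrt(1 − r²).

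| r | Variance removed | Equivalent n per arm | Gain per arm | Interval narrower by |
|---|---|---|---|---|
| 0.2 | 4% | 30/0.96 = 31.25 | about 1 | 2% |
| 0.3 | 9% | 30/0.91 = 33.0 | about 3 | 5% |
| 0.4 | 16% | 30/0.84 = 35.7 | about 6 | 8% |

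If the 13.75 already includes the spread due to duration, power at 30 per arm rises from 86.1% to 87.8%, 89.5% or 92.6% when duration explains 5%, 10% or 20% of the variance.

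**3. How often the arms differ in stage.** Take two independent binomials with 35 per arm and probability 0.5. A gap of 20 points is 7 patients (7/35), and the chance of a gap that large or larger is 0.120. A gap of 15 points or more needs at least 6 patients, since 0.15 × 35 = 5.25; the chance is 0.188. With 30 per arm, a gap of 20 points or more has probability 0.155.

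**4. How far such a gap moves the estimate.** With a half-and-half split, the stage means differ by 2 × r × SD = 2 × r × 13.75 = 5.5, 8.25 or 11 degrees. A 20-point gap shifts the unadjusted difference by 0.20 times that: 1.1, 1.7 or 2.2 degrees. The standard error at 30 per arm is 13.75 × sqrt(2/30) = 3.55 degrees, so the shift is about 0.3, 0.5 or 0.6 of a standard error.

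**5. The shift over all randomisations.** It is centred on zero. Its 95% range is ±1.96 × r × 3.55 = ±1.4, ±2.1 or ±2.8 degrees, against the planned 11.

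**6. An arm-by-duration interaction.** With early and late halves there are four cells of 15. The standard error of the difference between the two stage-specific treatment effects is 13.75 × sqrt(4/15) = 7.1 degrees, twice that of the main comparison.

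**The case against.** The strongest reply is that nothing here is invalid. Randomisation balances duration in expectation, and the unadjusted test already allows for chance imbalance in its error term, so its type I error is unaffected. That stands.

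Several stronger readings are tempting and are not supported:
- A reader might infer that imbalance pushes the result towards a treatment benefit. It favours either arm with equal probability, and no section says whether a patient at 3 months or one at 24 gains more external rotation over a year.
- A reader might take the protocol to say that recovery is spontaneous over about 30 months. It says only that the condition is often described as self-limiting and that its mean duration is 30 months; it gives no recovery curve.
- A reader might take the remark on late stages as proof that duration predicts outcome. It concerns which treatment works when, and for mobilisation, which both arms receive. It makes stage a plausible factor and no more.
- A reader might conclude that the trial is underpowered. If open-ended entry added spread beyond 13.75, power at 30 per arm would fall to 84.4%, 82.4% or 77.8% with duration explaining 5%, 10% or 20% of variance. That supposes the source study's SD contains no duration spread, which the documents do not show.

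The criterion of 50% loss of external rotation also excludes largely recovered shoulders, which narrows the contrast between early and late patients. It restricts severity, however, and fixes neither duration nor the direction of change.

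Finally, baseline range of motion is the more obvious covariate, and the choice among covariates is partly judgement. That is fair, and it is why the two are best added together.

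**Conclusion.** The point holds as a modest matter of precision. Entry is open-ended in duration, the background makes duration a plausible predictor of recovery, and the fixed analysis cannot use it. The between-arm comparison is valid without adjustment but less precise than it need be.

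On the assumed correlations the gain lies between negligible and useful. At the upper end, about 6 patients per arm is slightly more than the attrition allowance of 35 − 30 = 5. At the lower end it is a single patient. Even the uncommon 20-point imbalance moves the estimate by well under one standard error. Both the correlations and the half-and-half stage split are assumptions; only the SD, the difference and the group sizes come from the protocol. This is a cheap improvement of low priority.

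**What to change.** Record symptom duration in months at screening. For the between-arm comparison, replace the one-way ANOVA in the Intervention and Data analysis sections with a prespecified ANCOVA. Wording such as: *The between-arm difference at each assessment will be estimated by ANCOVA with treatment arm, the baseline value of the outcome and symptom duration (log months) as terms.*

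Leave eligibility as it is. If an arm-by-duration interaction is reported, label it exploratory; with 70 patients it will be imprecise.

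The cost of the duration term is one degree of freedom, a number on the eligibility form instead of a tick, and some recall error, which would reduce the gain. Both the recording and the covariate should be settled before recruitment: duration not captured at entry can be recovered later only by recall, and a covariate chosen after the results are known would not be credible.

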**Exclusion Criteria**

Severe degeneration, or trauma involving the shoulder (ie, rheumatoid arthritis, osteoarthritis, history of injury to the labrum or articular cartilage or malignancies in the shoulder region, etc.).

Neurologic diseases such as stroke or peripheral nerve neuropathy.

Pain or disorders of the cervical spine, elbow, wrist, or hand.

Pregnancy, cardiac, respiratory, kidney, or circulatory problems pregnancy.

History of fractures, treatment, or surgery to the lumbar spine, thoracic spine, cervical spine, and upper limbs

Injection with corticosteroids in the affected shoulder in the preceding 4 weeks.

Subjects with diabetes mellitus will be accepted.

Inflammatory joint disease affecting the shoulder.

Bilateral frozen shoulder due to possible underlying systemic cause.

**Outcome Measures**

The primary outcome measure is shoulder range of motion (active and passive shoulder abduction, and active and passive shoulder external rotation) measured by smartphone inclinometer (clinometer plaincode). The secondary outcome measures will be functional outcome measures [measured by the quick Disabilities of the Arm, Shoulder and Hand (Quick DASH) questionnaire and pain [measured using a visual analogue scale (VAS)] and SF-12 and Oxford Shoulder Score (OSS).

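### The protocol defines its primary outcome in two conflicting ways, one movement against four measures, and names no primary visit

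*Protocol*

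**What the plan says.** - **Protocol, Sample size:** "Shoulder external rotation range of motion is considered as the primary outcome measure for the proposed study". Active or passive is not specified. The calculation is for one comparison at 0.05 with 85% power: "With a two tailed hypothesis, the minimum required sample size is 30 patients per group", raised to 35 for attrition.
- **Protocol, Outcome Measures:** "The primary outcome measure is shoulder range of motion (active and passive shoulder abduction, and active and passive shoulder external rotation". Function, pain, SF-12 and the Oxford Shoulder Score are listed separately as secondary.
- **Protocol, Intervention:** "Shoulder external rotation and abduction ROM will be measured and compared within and between groups", with neither movement ranked above the other. On timing: "Subjects will be assessed at baseline and at 3, 6, and 12 months". No visit is marked as primary.
- **Time references that might imply a primary visit:** in the source used for sizing, "shoulder external rotation was measured at baseline and at 12-week post intervention for the glenohumeral range of motion exercise group"; and for the treatment period in this trial, "Exercises will be given within the pain threshold limit twice a week for 12 weeks".
- **Protocol, Data analysis:** one-way ANOVA is applied to every outcome, with no ranking of measures or visits.

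**The concern.** The primary endpoint determines what the trial can claim, and the protocol gives it two definitions. Both sections call their choice the primary outcome measure, so the longer list cannot be read as a set of secondary measures. Even a reader who prefers the Sample size section cannot tell which variable is meant, because active and passive external rotation are treated elsewhere as distinct measurements. With three follow-up visits and none designated, a result on abduction, on either form of external rotation, or at any of the three visits could be presented as the primary result with some support from the text. That exposes the trial to selective reporting and to a type I error above the nominal 5%. The stated sample size also has no basis under the four-measure definition: no effect size is given for abduction, and alpha is not divided.

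**Working it through.** **1. The two definitions side by side**

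| Feature | Sample size section | Outcome Measures section |
|---|---|---|
| Movement | External rotation | External rotation and abduction |
| Active or passive | Not stated | Both, for each movement |
| Number of primary measures | One | Four |
| Primary visit | Not stated | Not stated |

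External rotation is primary in both. The outright conflict is over abduction. Active versus passive external rotation is an ambiguity: one section is silent and the other lists both.

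**2. Reproducing the stated sample size**

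Inputs from the Sample size section: 22 (SD 12.5) and 33 (SD 14.9) degrees, two-sided alpha 0.05, power 85%.

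- Pooled SD = √[(12.5² + 14.9²)/2] = 13.75
- d = (22 − 33)/13.75 = −0.800 (stated as −0.799)
- Two-sample t test (noncentral t): n = 29.06 per group at d = 0.79986, or 29.12 at d = 0.799. Either rounds up to 30.
- Power: 86.1% at 30 per group and 91% at 35.

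The figure of 30 is therefore right for one test of one measure.

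**3. What other readings would imply**

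The protocol states no success rule and no correlations. The rates below take each possible reading in turn and assume equal correlation among the measures or visits. They come from simulated two-sample t tests at 30 per group (100,000 trials per setting). The independence values are exact.

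| Reading, each test at unadjusted 0.05 | False-positive rate | Assumed correlation | If independent |
|---|---|---|---|
| Active or passive external rotation, one visit | 7% to 9% | 0.9 to 0.5 | 1 − 0.95² = 9.8% |
| Any of four measures, one visit | 9% to 16% | 0.9 to 0.5 | 1 − 0.95⁴ = 18.5% |
| One measure at any of three visits | 10% to 13% | 0.8 to 0.4 | 1 − 0.95³ = 14.3% |

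Repeat simulations agreed to within about half a percentage point. For any of four measures at correlation 0.5 they gave 15.3% to 15.8%.

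The opposite rule, that all four must reach significance, does not inflate type I error but costs power. With d = 0.799 assumed on every measure, power is about 66% to 78% at 30 per group and about 76% to 85% at 35 (correlation 0.5 to 0.9).

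**4. Keeping all four as primary with a Bonferroni split**

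Alpha per measure = 0.05/4 = 0.0125. At d = 0.799 the t test needs 40.7, so 41 per group, for 85% power on each measure. Power per measure would be 69.6% at 30 and 77.9% at 35. The planned 35 per group therefore does not support this option at 85% power.

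**5. The primary visit**

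The treatment period is 12 weeks, the sizing source measured at 12 weeks and the first follow-up is at 3 months. These point towards 3 months. But the first describes the treatment schedule and the second describes another study. Neither sentence designates an endpoint for this trial.

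**The case against.** The strongest counter-arguments concern scope.

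- **The conflict is narrower than one against four.** External rotation is primary in both sections, so the true contradiction is the status of abduction, and active versus passive is only an ambiguity. This is correct as a description. It does not resolve the problem, because the single primary variable still cannot be identified from the text.
- **The primary visit could be left to an analysis plan that is not shown, and the text hints at 3 months.** No two sections conflict on the visit, so alone this would be a weaker point. It matters here because it widens an endpoint that is already contradictory. An analysis plan can add a multiplicity rule, but if it agreed with one section on the primary outcome it would contradict the other.
- **The error rates and power figures rest on rules the protocol never states.** This stands. The any-of-four and all-of-four rules exclude each other, the correlations are assumed, and no effect size for abduction is given. The figures show how far the readings differ and are not properties of the plan. It is also fair to quote power at the 35 recruited as well as at 30, as is done above.
- **Several primary measures with a stated multiplicity rule would also be valid.** In principle, yes. On the protocol's own effect size a Bonferroni version needs about 41 per group, more than the 35 planned, so it is not a change of wording alone.

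**Conclusion.** The concern holds and must be fixed. The Sample size and Outcome Measures sections give incompatible primary outcomes, no section reconciles them, and no visit is designated. The conflict lies inside the protocol, so an unseen analysis plan does not excuse it. This conclusion comes from the text and needs no assumption.

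The size of the consequence does rest on assumptions, namely the success rule, equal correlations and, for power, the same effect on every measure. Under them the false-positive rate rises from 5% to between 7% and 16%, depending on the reading, or power for an all-four rule falls below the planned 85% at 30 per group.

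That 30 per group reproduces shows only that the arithmetic fits one test. It does not show that d = 0.8 is a sound between-group effect, since the two means appear to be baseline and 12-week values from one arm of the cited study.

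**What to change.** Before any outcome data are compared by group, amend the Sample size, Intervention and Outcome Measures sections so that they agree on:

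- one external rotation measure, stated as active or passive, at one named visit, as the sole primary endpoint, tested once at two-sided 0.05;
- all other range-of-motion measures and visits as secondary, reported as estimates with confidence intervals;
- the point from which the visit months are counted. The Sample size section's description of its source as 12 weeks post intervention could mean the end of a 12-week programme or 12 weeks after it, so it does not settle which visit here corresponds.

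The sponsor should choose the measure and the visit; passive external rotation at 3 months is one option. If the sponsor prefers to keep four primary measures, the protocol needs a stated multiplicity rule and a sample size to match.

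The cost of the single-endpoint amendment is wording only, with no extra visits, measurements or patients, and the planned 35 per group still covers the single test on the protocol's own effect size. The price is that abduction and the other visits can no longer be claimed as primary. Once outcomes have been compared by group, the same change would have to be reported as post hoc.
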